9.2.3.3 Exploratory Endpoints

Assessment on symptoms based on the diary of subjects.

- The proportions (%) of subjects who have not been awakened during sleep for heartburn or acid regurgitation for the first 7 days, full 4 weeks, and full 8 weeks after the first IP administration and its 95% confidence interval will be presented by treatment group. To compare the control group and study group, the 2-sided 95% confidence intervals and p-value will be obtained by using the Cochran-Mantel-Haenszel method.
- The proportions (%) of subjects who have relieved from chronic cough for the first 7 days, full 4 weeks, and full 8

weeks after the first IP administration and its 95% confidence interval will be presented by treatment group. To compare the control group and study group, the 2-sided 95% confidence intervals and p-value will be obtained by using the **Chi Square test or Fisher's Exact test method**.

- The proportions (%) of subjects who have relieved from foreign body sensation for the first 7 days, full 4 weeks, and full 8 weeks after the first IP administration and its 95% confidence interval will be presented by treatment group. To compare the control group and study group, the 2-sided 95% confidence intervals and p-value will be obtained by using the **Chi Square test or Fisher's Exact test method**.

(Week 8 evaluation will only be applicable to patient receiving treatment 2)

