8.3.14 Distribution and Collection of Subject Diary

The subject diary will be distributed at Visit 2 and the training on how to complete it will be provided. The completion status of the subject diary will be checked at Visit 3 via site visit, and appropriate training on the diary keeping will be performed, if necessary. At Visit 4, the completed subject diary will be collected and the subjects who have not symptoms relief will be prescribed the IP for Treatment 2 and the subject diary will be re-distributed to the subject. At Visit 5, the subject diary will be collected only from those who have undergone Treatment 2. Assessment of symptoms and treatment compliance will be done based on the subject diary

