8.4.1.3 Exploratory Endpoints

Assessment on symptoms based on the diary of subjects.

- Proportions of subjects who have not been awakened during sleep for heartburn or acid regurgitation for first 3 days, 7 days, 4 weeks, and 8 weeks (or based on the day Investigator's need) after the first IP administration.

- Proportions of subjects who have relieved from chronic cough for first 3 days, 7 days, 4 weeks, and 8 weeks (or based on the day Investigator's need) after the first IP administration daytime and nighttime.
- Proportions of subjects who have relieved from irritating feeling in the throat for full 3 days, 7 days, 4 weeks, and 8 weeks (or based on the day Investigator's need) after the first IP administration daytime and nighttime.
(Week 8 evaluation will only be applicable to patient receiving treatment 2)

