8.4.2.2 Assessment on symptoms based on the diary of subjects

The subjects will self-assess each symptom of 'heartburn' and 'acid regurgitation' (major symptoms of gastroesophageal reflux disease) twice daily (daytime/nighttime combined) in the subject diary which then will be collected and analyzed. In addition, the presence of 'chronic cough' and 'foreign body sensation in the throat' which are non-typical symptoms of gastroesophageal reflux disease will be assessed twice daily (daytime/nighttime combined), and any experience of awakening during sleep for heartburn or acid regurgitation will be collected.

The scale (0 to 4) for scores of assessing daytime/nighttime combined symptoms of 'heartburn' and 'acid regurgitation' is as follows:

Assessment on daytime symptoms		
0	None	No symptoms
1	Mild	Symptoms noticeable, but not bothersome
2	Moderate	A little bothersome and some limitations of daily activities
3	Severe	Symptoms noticeable for a lot of time and frequent limitations of daily activities
4	Very severe	Symptoms persistent and considerable limitations of daily activities

Assessment on nighttime symptoms		
0	None	No symptoms
1	Mild	Symptoms noticeable, but can be ignored, and do not disturb sleep
2	Moderate	A little bothersome and some disturbance of sleep
3	Severe	Symptoms noticeable for a lot of time and frequent disturbance of sleep
4	Very severe	Symptoms persistent and difficulties in sleeping

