Refluks asam lambung	 Tidak ada  Ringan  Sedang  Berat  Sangat berat		Refluks asam lambung	 Tidak ada  Ringan  Sedang  Berat  Sangat berat	
Batuk kronis	 Tidak  Ya		Batuk kronis	 Tidak  Ya	
Sensasi mengganggu di tenggorokan	 Tidak  Ya		Sensasi mengganggu di tenggorokan	 Tidak  Ya	
			Pernahkah Anda terbangun dari tidur karena gejala “nyeri ulu hati” atau “refluks asam lambung”?	 Tidak  Ya	

Memo

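### Relief of chronic cough and of throat sensation has no designated baseline, no definition and no restricted denominator, so the endpoints measure absence of the symptom and dilute any difference

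*Combined protocol and SAP*

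**What the plan says.** Section 8.4.1.3 lists among the exploratory endpoints "Proportions of subjects who have relieved from chronic cough for first 3 days, 7 days, 4 weeks, and 8 weeks", counted from the first dose, with a parallel item for an irritating feeling in the throat. The analysis in Section 9.2.3.3 gives "The proportions (%) of subjects who have relieved from chronic cough for the first 7 days" and "The proportions (%) of subjects who have relieved from foreign body sensation for the first 7 days", plus the full 4- and 8-week windows, by treatment group, compared by chi-square or Fisher's exact test. None of these places says what makes a subject relieved or which subjects form the denominator.

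Section 8.4.2.2 says how the symptoms are measured. Their presence is noted, and cough and throat sensation, "which are non-typical symptoms of gastroesophageal reflux disease will be assessed twice daily", have no severity scale. On the diary page in Attachment 4, the cough item and the throat item ("Sensasi mengganggu di tenggorokan") each offer only no or yes, once for day and once for night.

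On timing, Section 8.3.14 states: "The subject diary will be distributed at Visit 2 and the training on how to complete it will be provided". Sections 7.2.2 and 8.3.13 start dosing on the day after dispensing.

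**The concern.** Relief means that a symptom was present and then went away. To establish it, one must know who had the symptom before treatment. The plan keeps this distinction elsewhere. For heartburn and regurgitation it counts subjects without symptoms, for sleep it counts subjects not woken, and for GERD-Q and GERD-HRQL it takes change from a baseline. Only cough and throat sensation are described as relieved, and they have no planned baseline behind the word.

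An analyst working from Section 9.2.3.3 must either treat every all-'no' diary as relief or invent a baseline rule after the data are in. Under the first choice, subjects who never coughed raise the percentage in both arms and shrink the difference between them. A high figure could then be reported as relief when most of it reflects subjects who had nothing to relieve. A baseline that was not collected systematically before dosing cannot be recovered at analysis.

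**Working it through.** **1. Is there a baseline anywhere in the plan?**

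- Diary: first handed out at Visit 2; there is no run-in diary (Sections 8.2 and 8.3.14).
- GERD-Q (Attachment 2): six items, none on cough or throat sensation.
- GERD-HRQL (Attachment 3): it covers heartburn, swallowing, bloating, medication and satisfaction, but neither of these symptoms.
- Eligibility (Section 3.2): heartburn and/or regurgitation only.
- Medical history (Section 8.3.4): ongoing clinically significant conditions. It is not systematic for these symptoms and not linked to the endpoints.

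So no baseline is designated.

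**2. The plan's own figure.** The documents give no figure for these two endpoints. The only sample size is for the primary endpoint (Section 9.4.2). It reproduces, and it supplies the arm size used below. With rates 0.94 and 0.885, margin 0.1 and n = 53 per group:

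- pooled SE = √(2 × 0.9125 × 0.0875 / 53) = 0.05489
- unpooled SE = √((0.94 × 0.06 + 0.885 × 0.115) / 53) = 0.05463
- power = Φ[(0.155 − 1.96 × 0.05489) / 0.05463] = Φ(0.868) = 0.807, against 0.80729 stated
- 53 / 0.8 = 66.25, so 67 per group and 134 in total

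**3. Dilution.** Let q be the share with the symptom at baseline and r the relief rate among them. Suppose subjects without the symptom count as relieved and do not develop it. Then

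- rate in an arm = (1 − q) + q·r
- difference between arms = q·(r_T − r_C)

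Neither q nor r is in the documents, so all values below are assumptions. For a 20-point benefit, taken as 50% against 30%:

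| q | Study group | Control group | Difference | Never symptomatic |
|---|---|---|---|---|
| 10% | 95.0% | 93.0% | 2 points | 90% |
| 20% | 90.0% | 86.0% | 4 points | 80% |
| 40% | 80.0% | 72.0% | 8 points | 60% |

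At q = 10%, 90 of the 93 percentage points in the control group come from subjects who never had the symptom.

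**4. Power**, two-sided 5%, 67 per arm, assumed relief 60% against 30% among symptomatic subjects (chi-square / Fisher):

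| q | All subjects: difference | All subjects: power | Symptomatic only: n per arm | Symptomatic only: power (30 points) |
|---|---|---|---|---|
| 10% | 3 points | 0.12 / 0.05 | 7 | 0.19 / 0.08 |
| 30% | 9 points | 0.29 / 0.22 | 20 | 0.48 / 0.35 |
| 50% | 15 points | 0.49 / 0.42 | 34 | 0.71 / 0.62 |
| 70% | 21 points | 0.71 / 0.65 | 47 | 0.84 / 0.79 |

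In these cases restriction loses no power despite the smaller groups. With a 40-point benefit and q = 50%, the diluted comparison still has power 0.77 / 0.72.

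**The case against.** A reader might infer that the endpoint cannot show an effect at all. The tables do not support that: the difference is attenuated by q, and a large benefit with a common symptom would still be found with reasonable power.

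A reader might also take it as a rule of the plan that subjects who never had the symptom count as relieved. The text sets no such rule, and the word relieved could be read as presupposing the symptom. Counting them is the natural outcome of a yes/no diary with an open denominator, but it remains an inference.

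A third stronger reading is that any baseline imbalance would pass for a drug effect. Allocation is randomised 1:1, and chance imbalance is already reflected in the planned confidence interval and p-value. Comparing symptom-free proportions between arms is valid; it is less sensitive and wrongly named.

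Pre-dose information is not wholly absent. Because dosing starts the day after dispensing, a diary entry before the first dose is possible, and medical history could pick up an ongoing cough. Neither is designated as a baseline, and neither would give a systematic one for both symptoms.

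Two further points stand. The size of the dilution rests entirely on assumed prevalence and relief rates; at 70% prevalence it is mild. At 10% prevalence, restriction leaves about 7 per arm and little power either way, so the gain there is a number that means what it says, not a more powerful test.

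**Conclusion.** The point holds as a defect of definition and data collection. The plan designates no baseline, gives no definition of relief and does not limit the denominator. Under the plan as written, relief cannot be told apart from never having had the symptom, and the endpoints in effect report absence during treatment.

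The true difference is multiplied by q, which gives the 2, 4 or 8 points shown above for a 20-point benefit. These figures assume that subjects without the symptom are counted as relieved and stay free of it throughout the window. The documents support neither a claim that an effect is undetectable nor a claim that the comparison is biased.

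The consequence is limited. Both endpoints are exploratory, and the primary non-inferiority conclusion and the sample size are untouched. This is a cheap improvement worth making, not an obstacle to the trial.

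**What to change.** 1. At Visit 2, before the first dose, ask the two existing yes/no items (cough, throat sensation) once, with a stated recall period such as the last 7 days.
2. Define relief in Sections 8.4.1.3 and 9.2.3.3 as 'yes' at baseline and 'no' in all diary entries over the stated window.
3. Report the proportion among subjects with the symptom at baseline, giving that denominator by arm.
4. If a baseline can no longer be collected, rename the endpoints as subjects without cough and subjects without throat sensation, and describe them that way in the report.

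The cost is two tick-boxes, a definition and a change of denominator. The downside is smaller exploratory subgroups: with 67 per arm, about 7 per arm at an assumed 10% prevalence and 13 at 20%. The 8-week groups would be smaller still, because that evaluation covers only subjects who enter Treatment 2.

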9.2.4 Safety Endpoints

Safety analysis will be conducted using the safety sets, based on AEs, vital sign abnormalities, laboratory abnormalities, physical examination abnormalities, etc.

9.2.4.1 Adverse events

AEs will be recorded based on worsening of existing symptoms or the newly occurring treatment-emergent adverse events (TEAEs) after administration of the IP.

For TEAEs, adverse drug reactions (ADRs), and serious adverse events (SAEs), descriptive statistics (number of subjects, incidence (%), and number of cases) will be presented, and Chi-square test or Fisher's exact test will be used for analysis depending on whether cells with the expected frequency of <5 is $>20\%$ or not.

AEs, ADRs, and SAEs will be coded by system organ class (SOC) and preferred term (PT) using the medical dictionary for regulatory activities (MedDRA) version 21.0 (or higher), and coded AEs will be presented with the number of subjects, incidence, and the number of cases by treatment group. The frequency and percentage of subjects who are withdrawn due to serious adverse events or AEs will be presented and the listings will be provided.

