Study Methodology	
Subjects will be provided a written informed consent to participate in the study and then undergo any screening. If a subject is taking any drug that affects the gastric mucosa at the time of screening, the treatment will be start after washout period of up to 2 weeks. Subjects who meet all of the inclusion criteria and none of the exclusion criteria based on the screening test results will be randomized.
 
Overall, the subjects will receive treatment for a duration of 4 ~ 8 weeks., The subjects will take 1 tablet/capsule of the investigational product (IP) once daily (1 tablet of Fexuprazan 40 mg or 1 capsule Esomeprazole 40 mg according to randomization). Initially, the subject will received the IP for 1 week at Visit 2 (Day 0). Subject will visit the study site at Visit 3 (Day 7 ± 5 days) for early evaluation and will be prescribed for another 3 weeks of IP. Subjects will visit the study site at Visit 4 (Day 28 ± 5 days) to determine healing status through symptom relief. Healed subjects after 4 weeks of treatment will have a Safety Follow-Up (F/U) visit after 2 weeks, while unhealed subjects will continue with an additional 4 weeks of treatment. After unhealed subjects have completed a total of 8 weeks of treatment at Visit 5 (Day 56 ± 5 days), they will have a Safety F/U visit after 2 weeks. (This Safety F/U will be conducted over the phone. If necessary, additional examination and treatment may be performed according to the investigator's judgment.)

Figure 1. Study Schematic

Inclusion Criteria	
Subjects must meet all the following criteria:
 
 1) Male and female adults aged 18 to 60 years at the date of the written informed consent form. 2) Those who had experienced heartburn and/or acid regurgitation confirmed with: 
 ➢ GERD-Q Score >7 and ➢ People who have experienced heartburn symptoms > 3 days within the last 7 days, or ➢ People who have experienced acid reflux (symptom of acid reflux or back flowing of contents from stomach into the esophagus) > 3 days within the last 7 days 3) Those who could understand the provided information and able to fill out the questionnaire and subject diary. 4) Those who voluntarily decided to participate in the study and wrote the informed consent form.

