4.1 Study Period

- Study duration: Approximately 14 months from IRB approval to completion
- Study duration for each subject: 8-12 weeks
 - Screening period: Up to 2 weeks
 - Treatment period: Up to 4 weeks (unhealed subject will continue additional 4 weeks of treatment)
 - Follow-up period: For 2 weeks from the last dose

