5.1 Scheduled Completion

If all protocol-specified procedures and assessments are completed after the IP administration, the subject will be considered to have completed the study. Subjects with symptoms relief at Week 4 measured by GERD-Q Score <8 will have the Safety F/U after 2 weeks from the date and be terminated from the study.

In this study, completion of the last subject is defined as the end of study.

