8.5.2.2 Criteria and Method for Adverse Event Assessment

Confirmed information such as occurrence of adverse event (AE), AE term, severity of AE, date of onset and resolution, relationship to the investigational product, action taken, treatment, and outcome will be recorded on the case report form.

Any laboratory abnormality and abnormal finding in physical examination or vital signs that are considered clinically significant will be recorded as AEs.

Adverse event (AE) from the first IP administration to safety follow up visit (visit 4-1 or 5-1) must be recorded regardless of its relationship with the IP. At each visit after IP administration, the following methods may be done to identify AEs:

- Information provided by subject or legal guardian without any prompt
- At each visit, asking open-ended and non-suggestive questions
- Abnormalities observed by the investigator, other medical professionals and relatives.

Except for lost to follow-up, AEs (including AEs unresolved until the completion of the study) will be monitored, if possible, until the AEs recover to the pre-dose state or to the baseline, or the investigator determines that the AEs have normalized or further monitoring is unnecessary.

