9.1 Analysis Sets

Per Protocol Set (PPS)

The PPS will include the subjects in the FAS who complete the study without any major protocol deviation. Major protocol deviations include 'violation of the inclusion and exclusion criteria', 'administration of prohibited concomitant medications during the study', etc. (see Section "13.5 Protocol Deviations"), and the subjects with other major deviations will be determined at the case report adjudication meeting prior to disclosure of randomization codes.

Full Analysis Set (FAS)

The FAS will include the subjects who receive the IP at least once after randomization and who have at least one efficacy assessment result. The subjects who violate the inclusion/exclusion criteria will be excluded from the FAS.

For the efficacy analysis, they will be included in the randomized treatment group regardless of the actual IP taken.

Safety Set

The safety set will include all the subjects who receive the IP at least once after randomization. The subjects who are enrolled in the study but withdrawn from the study before IP administration will be excluded from the safety set. For the safety analysis, the subjects will be analyzed according to the treatment they actually received.

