9.4.2 Rationale for Determination of Sample Size

This study objective is to determine the non-inferiority of the study group (Fexuprazan 40 mg) compared to the control group (Esomeprazole 40 mg) in patients with erosive gastroesophageal reflux disease. The primary endpoint is the proportions of subjects with symptoms relief at week 4 measured by GERD-Q Score <8 , and the hypothesis is:

$$H_0: \pi_T - \pi_C \leq -0.1 \quad \text{vs.} \quad H_A: \pi_T - \pi_C > -0.1$$

π_T : Proportion of subjects with symptoms relief at week 4 (measured by GERD-Q score <8) in the study group (Fexuprazan 40 mg)

π_C : Proportion of subjects with symptoms relief at week 4 (measured by GERD-Q score <8) in the control group (Esomeprazole 40 mg)

The proportion of subjects with symptoms relief at week 4 of proton pump inhibitors (PPI) was considered to be 88.5%, and this value was set as the proportion of symptoms relief for the control group (Esomeprazole 40 mg). In this study, the proportion of symptoms relief of the study drug was assumed to be higher than control drug, therefore, 94.0% was set as the proportion of symptoms relief in the study group.

The number of subjects calculated by “Non-Inferiority Tests for the Difference Between Two Proportions” of PASS2020 with the non-inferiority margin of -0.1, the one-sided significance level of 2.5%, 80% statistical power, and 1:1 randomization allocation, was 53 per group. And considering a dropout rate of 20%, a total of 134 subjects will be enrolled in the study.

Non-Inferiority Tests for the Difference Between Two Proportions											
Numeric Results											
Test Statistic: Z-Test with Pooled Variance											
Hypotheses: H0: P1 - P2 ≤ D0 vs. H1: P1 - P2 > D0											
Target Power	Actual Power*	N1	N2	N	Ref. P2	P1 H0 P1.0	P1 H1 P1.1	NI Diff D0	Diff D1	Alpha	
0.80	0.80729	53	53	106	0.8850	0.7850	0.9400	-0.1000	0.0550	0.025	
* Power was computed using the normal approximation method.											

10 Data Management (Recording, Collection, Access, Protection, and Storage)

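### Adverse-event incidence is tested between arms over follow-up that lasts about 6 weeks if relieved at Week 4 and about 10 if not; the resulting bias is small at the planned rates but easy to remove

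*Combined protocol and SAP*

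**What the plan says.** **Length of follow-up.** Section 4.1 gives "Treatment period: Up to 4 weeks (unhealed subject will continue additional 4 weeks of treatment", followed by two weeks of follow-up. The synopsis (Study Methodology) sets out the two paths. For the first, "Healed subjects after 4 weeks of treatment will have a Safety Follow-Up (F/U) visit after 2 weeks". For the second, "After unhealed subjects have completed a total of 8 weeks of treatment at Visit 5", the safety contact comes two weeks later. The schedule of activities puts these contacts at Day 42 (Visit 4-1) and Day 70 (Visit 5-1), each ±5 days. Section 5.1 confirms that subjects relieved at Week 4 "will have the Safety F/U after 2 weeks from the date and be terminated from the study".

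**Event collection.** Section 8.5.2.2 states: "Adverse event (AE) from the first IP administration to safety follow up visit (visit 4-1 or 5-1) must be recorded". The collection window therefore closes at whichever contact the Week 4 result leads to.

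**Analysis.** Section 9.1 pools both paths: "The safety set will include all the subjects who receive the IP at least once after randomization". Section 9.2.4.1 then specifies, for TEAEs, ADRs and SAEs, "descriptive statistics (number of subjects, incidence (%), and number of cases) will be presented, and Chi-square test" or Fisher's exact test, depending on expected cell counts. The synopsis says less. It gives the frequency and percentage of subjects with at least one event by group, with 95% confidence intervals, and has neither event counts nor a between-arm test.

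No section provides person-time, an exposure-adjusted rate, a time-to-event analysis of adverse events, or separate tables for Treatment 1 and Treatment 2.

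**The concern.** Whether a subject is followed for 6 or 10 weeks, and treated for 4 or 8, is decided after randomisation by the outcome the trial compares. Randomisation therefore does not balance it. If one arm has more relief at Week 4, it contributes less time at risk and less time on drug. Its crude incidence and event count are then lower even with the same event rate per week. Section 9.4.2 expects that arm to be fexuprazan; the direction would reverse if esomeprazole did better.

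What is at stake is how the safety table is read. Safety is named in the study title and in the synopsis objective. A reader of a tested difference in percentages will usually take it as a difference in tolerability per unit of exposure, which this table does not isolate.

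**Working it through.** **Inputs from the plan**
- Relief at Week 4: 88.5% control, 94.0% study group (Section 9.4.2).
- Follow-up: 4 + 2 = 6 weeks if relieved, 8 + 2 = 10 weeks if not. Planned treatment: 4 or 8 weeks.
- Arm size: 67. The sample size reproduces. The pooled-variance Z formula gives power 0.7998 at 52 per group and 0.8073 at 53 (stated 0.80729), and 53/0.8 = 66.25, rounded up to 67 per arm, 134 in total.
- Phase 2 event risk: 36 of 156 fexuprazan-treated subjects (Section 13.8.1), all doses pooled, in erosive disease.

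**Assumptions**
- The same constant event hazard in both arms, on and off drug.
- The phase 2 risk was accrued over 8 weeks. Section 1.4 gives treatment of up to 8 weeks but no event observation time.
- No dropout, and visits on their nominal days.
- Every subject not relieved continues to Treatment 2. The synopsis defines non-healed as GERD-Q above 8 and relief as below 8, which leaves a score of exactly 8 unassigned; those passages must be reconciled.

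**Formulas**, with p the proportion relieved
- Mean follow-up = 6p + 10(1 - p). Mean planned treatment = 4p + 8(1 - p).
- Crude incidence = p·r6 + (1 - p)·r10, where r6 and r10 are the 6- and 10-week risks.
- Spurious difference = (p_T - p_C)(r6 - r10).

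**Hazard.** h = -ln(1 - 36/156)/8 = 0.0328 per week, so r6 = 1 - exp(-6h) = 17.86% and r10 = 1 - exp(-10h) = 27.96%.

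| Relief, study vs control | Mean follow-up (weeks) | Ratio | Mean treatment (weeks) | Crude incidence | Difference (points) |
|---|---|---|---|---|---|
| 94.0% vs 88.5% (plan) | 6.24 vs 6.46 | 0.966 | 4.24 vs 4.46 | 18.47% vs 19.02% | about -0.55 |
| 80% vs 70% (assumed) | 6.8 vs 7.2 | 0.944 | 4.8 vs 5.2 | 19.88% vs 20.89% | about -1.0 |
| 70% vs 50% (assumed) | 7.2 vs 8.0 | 0.900 | 5.2 vs 6.0 | 20.89% vs 22.91% | about -2.0 |

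Event counts shift in proportion to follow-up, so by 3.4% at the plan's rates.

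**Sensitivity to the event risk.** At the plan's relief rates, with r6 assumed and r10 = 1 - (1 - r6)^(10/6):
- r6 = 10%: r10 = 16.1%, crude incidence 10.4% vs 10.7%, difference about -0.3 points.
- r6 = 40%: r10 = 57.3%, crude incidence 41.0% vs 42.0%, difference about -1.0 points.

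**Size against noise.** At the plan's rates about 67 × 0.06 = 4.0 and 67 × 0.115 = 7.7 subjects enter Treatment 2. The -0.55 points equals about 0.4 of a subject in 67. The standard error of the difference near 19% incidence is sqrt(2 × 0.19 × 0.81/67), about 6.8 points, so the bias is about 0.08 standard errors. Over r6 from 10% to 40%, the chance of a false significant result moves from 5.0% to 5.0-5.1%. At an assumed 70% vs 50% relief it is 5.5% to 6.9%.

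**Check on the remedy.** Under the same assumptions, an exposure-adjusted rate or a Day 0-28 window gives a between-arm ratio of 1.00.

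**The case against.** The strongest reply is that crude incidence by randomised arm is a legitimate quantity. It measures the event burden of the whole regimen, including four more weeks of drug for those who need them. A less effective drug that leads to longer treatment does produce more events. This stands: a reader might infer that the safety comparison is confounded with efficacy and therefore invalid, but extension is a consequence of assigned treatment, not a confounder. The fair criticism is that the plan does not say which question its test answers and offers nothing for the per-exposure question.

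Materiality is also limited. No safety hypothesis is powered or given a margin; the only hypothesis is Week 4 non-inferiority (Section 9.3). The larger differences rest on relief rates of 80% vs 70% and 70% vs 50%, which appear nowhere in the documents.

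Nor is the period to Visit 4 perfectly equal for everyone. The plan allows for 20% dropout, withdrawn subjects have a Withdrawal visit instead, and Visit 4 has a ±5-day window. Restricting to that period removes the response-driven part of the imbalance, but person-time is still needed for the rest.

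On the other side, the equal-hazard calculation omits a difference in detection. Unrelieved subjects have one more in-person visit with examination and laboratory tests (Visit 5), while the planned contact for relieved subjects after Visit 4 is by telephone. The documents give no figure from which to size this.

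**Conclusion.** The point holds as a minor gap in the safety analysis. Section 9.2.4.1 tests crude incidence over follow-up whose length depends on the Week 4 result, with no exposure adjustment and no Treatment 1 table. The direction is predictable: the arm with more relief appears to have fewer events.

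At the plan's own relief rates the artefact is about -0.55 points, or 0.3 to 1.0 points across assumed 6-week risks of 10% to 40%. It does not shrink with sample size, and it grows with the relief gap. These figures rest on an equal, constant hazard and no dropout.

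A reader might infer that the trial is likely to declare fexuprazan falsely safer. The numbers do not support that: the false-positive rate barely moves at the planned rates. A reader might also infer that the synopsis tests event counts between arms; it does not, and the test is in Section 9.2.4.1 alone. The primary efficacy conclusion is unaffected.

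**What to change.** Keep the crude whole-study table, labelled as a description of each regimen's event burden, and add to Section 9.2.4.1:

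- **(a)** a between-arm comparison of TEAEs, ADRs and SAEs with onset in Treatment 1, from first dose to Visit 4 or earlier withdrawal. A Day 42 cut-off would not serve, because Days 28-42 are off drug for relieved subjects and on drug for the others;
- **(b)** exposure-adjusted rates for the whole study: subjects with a first event, and events, per 100 subject-weeks, with person-time ending at withdrawal;
- **(c)** a descriptive table of events after Visit 4, split into post-treatment follow-up (relieved) and Treatment 2 plus follow-up (unrelieved), without a between-arm test.

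State that p-values from the crude whole-study table are descriptive because follow-up depends on response.

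The cost is analysis-plan wording and a few extra tables from onset dates that Section 8.5.2.2 already requires. No visit, procedure or sample-size change is needed. The limitation is that an exposure-adjusted rate assumes a roughly constant hazard, so it should stand beside the crude table and not replace it.
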